#### ***Last Observation Carried Forward (LOCF)***

Intermediate missing data and missing data after discontinuation of study drug during the DB RWP will be imputed using the last non-missing daily number of cataplexy attacked collected prior to the daily missing data using a LOCF approach. Average weekly number of cataplexy attacks during the DB RWP will then be computed and the primary analysis model will be repeated.

#### **9.8.1.6. SUBGROUP ANALYSIS OF PRIMARY EFFICACY ENDPOINT**

Subgroup analyses for groups specified in [section 7.5](#) will be performed for the primary efficacy endpoint. These subgroups will be analyzed similarly to the primary efficacy analysis with the exception that for the Pre-randomization Group subgroup analyses, the Pre-randomization Group fixed effect will be excluded from the ANCOVA models.

A forest plot including each subgroup by randomized treatment group will also be provided.

### **9.8.2. KEY SECONDARY EFFICACY ENDPOINTS**

#### **9.8.2.1. KEY SECONDARY EFFICACY ENDPOINT-& DERIVATION**

The key secondary efficacy endpoint is the change in ESS score from the end of the OL SDP to the end of the DB RWP.

The ESS is a self-administered questionnaire with 8 questions/ items asking the subjects how likely they would be to doze off or fall asleep in different situations (Johns 1991, Broderick et al 2013). Responses range from 0 = would never doze to 3= high change of dozing. Subjects will be asked to complete the ESS with regard to the level of sleepiness they experienced over the past 7 days at the end of the OL SDP and at the end of the DB RWP.

The ESS total score is the sum of the 8 item-scores and can range between 0 and 24. Higher scores indicate greater daytime sleepiness. If three or more item scores are missing at a specific time point, the ESS total score will be set to missing. If one or two ESS item scores are missing at a specific time point, the mean of the remaining seven or six non-missing ESS item scores at that time point will be used to impute the missing ESS item scores. The ESS total score will be then calculated as the sum of the observed and imputed item scores.

#### **9.8.2.2. MISSING DATA METHODS FOR KEY SECONDARY EFFICACY ENDPOINT**

For subjects without post-randomization ESS data, the result from the OL SDP will be carried forward using a BOCF approach.

#### **9.8.2.3. ANALYSIS OF KEY SECONDARY EFFICACY ENDPOINT**

The ESS total score will be summarized and analysed similarly to the primary efficacy endpoint (refer to [section 9.8.1.4](#)).

#### **9.8.2.4. SENSITIVITY ANALYSIS OF KEY SECONDARY EFFICACY ENDPOINT**

Sensitivity analyses will be performed similarly to the primary efficacy endpoint (see [section 9.8.1.5](#)). The sensitivity analysis to the missing data assumption using LOCF will not be performed as only one post-randomization ESS assessment was performed.

An additional sensitivity analysis to the use of stimulant during the OL SDP will be performed using the same ANCOVA model as for the primary efficacy endpoint, but adjusted for the stimulant use i.e., a binary

variable (“yes” if the subject takes at least one dose of stimulant during the SDP, “no” otherwise) will be added to the model as a covariate. Stimulant medications are listed in [APPENDIX 3](#).

### **9.8.2.5. SUBGROUP ANALYSIS OF KEY SECONDARY EFFICACY ENDPOINT**

Subgroup analyses will be performed in the same manner as the subgroup analyses for the primary efficacy endpoint (see [section 9.8.1.6](#)).

An additional subgroup analysis for stimulant use subgroup (“yes” if the subject takes at least one dose of stimulant during the SDP, “no” otherwise) will be performed in the same manner as the subgroup analyses for the primary efficacy endpoint (see [section 9.8.1.6](#)). Stimulant medications are listed in [APPENDIX 3](#).

## **9.8.3. OTHER SECONDARY EFFICACY ENDPOINTS**

### **9.8.3.1. OTHER SECONDARY EFFICACY ENDPOINTS & DERIVATIONS**

#### **9.8.3.1.1. PGIC FOR NARCOLEPSY OVERALL AT THE END OF THE DB RANDOMIZED-WITHDRAWAL PERIOD**

A secondary efficacy endpoint is the PGIC for narcolepsy overall at the end of the DB RWP.

The PGIC is a 7-point Likert-type rating scale and a widely used assessment to assess efficacy in clinical drug trials. At the end of the DB RWP, subjects will rate the change in their condition on a 7-point scale ranging from 1 = “very much improved” to 7 = “very much worse” since the last visit i.e., end of the OL SDP.

#### **9.8.3.1.2. CGIC FOR NARCOLEPSY OVERALL AT THE END OF THE DB RANDOMIZED-WITHDRAWAL PERIOD**

A secondary efficacy endpoint is the CGIC for narcolepsy overall at the end of the DB RWP.

The CGIC is a 7-point Likert-type rating scale and a widely used assessment to assess efficacy in clinical drug trials. At the end of the DB RWP, Investigators will rate their impression of any change in the severity of the subject’s narcolepsy overall condition since the start of the DB RWP on a 7-point scale ranging from 1 = “very much improved” to 7 = “very much worse”.

#### **9.8.3.1.3. CHANGE IN SF-36 FROM END OF OL STABLE-DOSE PERIOD TO END OF DB RANDOMIZED-WITHDRAWAL PERIOD**

Another secondary efficacy endpoint is the change in SF-36 from the end of the OL SDP to the end of the DB RWP.

The SF-36v2 is a multi-purpose, short-form health survey with 36 questions/ items. It yields an 8-scale profile of functional health and well-being scores as well as a psychometrically-based physical and mental overall component summary measures. Subjects will complete the SF-36v2 with a one-week recall period at the end of the OL SDP and at the end of the DB RWP/ Early Termination visit.

The 8-scale profile of functional health and well-being scores are:

- Physical Functioning (PF)
- Role-Physical (RP)
- Bodily Pain (BPa)
- General Health (GH)
- Vitality (VT)
- Social Functioning (SF)
- Role-Emotional (RE)
- Mental Health (MH)

The two overall component summary measures are:

- Physical Component Summary (PCS)
- Mental Component Summary (MCS)

There is also a single item (item 2) that assesses health transition, which is not included in the scoring of the scales and overall component summary measures. Scoring will be performed with the Optum™ software as follows:

First, 10 items are reverse-coded and an algorithm for an algebraic summation of item scores is applied to produce domain-specific raw scales that account for missing item responses. Domain-specific raw scales are then transformed to a 0 to 100 range, after which a norm-based (T-score) transformation is applied so that each scale ranges from 0 to 100, with a mean of 50 and a standard deviation of 10 in the 1998 general U.S. population (Ware et al 2000). The norm-based transformation is applied so that domain-specific scales can be meaningfully compared between each other.

The mental and physical component summary scores (MCS/PCS) are computed by aggregating domain scores using factor score coefficients from the 1998 general U.S. population (Ware et al 2000). The aggregated summary scores are standardized to have a mean of 50 with a standard deviation of 10 in the general 1998 U.S. population (Ware et al 2000).

When calculating the raw domain scores, if at least half the item scores for a domain are non-missing, the missing item scores will be replaced with the average of the non-missing scores for the domain. Otherwise the raw domain score and corresponding norm-based domain scores will be set to missing.

#### **9.8.3.1.4. CHANGE IN EQ-5D-5L SELF-REPORTED QUESTIONNAIRE FROM THE END OF THE OL STABLE-DOSE PERIOD TO THE END OF DB RANDOMIZED-WITHDRAWAL PERIOD**

The last secondary efficacy endpoint is the change in EQ-5D-5L questionnaire from the end of the OL SDP to the end of the DB RWP.

Subjects will complete the EQ-5D-5L at the end of the OL SDP and the end of the DB RWP by selecting the most appropriate level in each of the 5 dimensions.

The EQ-5D-5L is a standardized instrument for use as a measure of health outcome that includes a

descriptive system consisting of 5 dimensions (mobility, self-care, usual activities, pain/ discomfort, and anxiety/ depression) (EuroQol Group, 2013). The EQ-5D-5L includes five levels of severity for each of the 5 dimensions of the descriptive system (1= no problems, 2= slight problems, 3= moderate problems, 4= severe problems, and 5= extreme problems) that reflect increasing levels of difficulty. The digits for these 5 dimensions will be combined in a 5-digit number describing the subject’s health state (e.g., 11122), for a total of 3125 possible health states. A scoring function will be used to assign a value (i.e., EQ-5D-5L index score) to self-reported health states from a set of population-based preference weights. Studies that directly elicit preferences from general population samples to derive value sets for EQ-5D-5L are under development in a number of countries; however, these studies will take some time to complete and for results to be disseminated. In the interim, the EuroQoL Group coordinated a study that administered both the 3-level and 5-level versions of the EQ-5D, in order to develop a ‘crosswalk’ between the EQ-5D-5L value sets and the EQ-5D-5L descriptive system, resulting in crosswalk index value sets for the EQ-5D-5L. As a result, crosswalk index values sets (see APPENDIX 4) are currently available for 10 countries: Denmark, France, Germany, Japan, the Netherlands, Spain, Thailand, United Kingdom, United States of America, and Zimbabwe. Subjects from countries without index values will be scored with neighboring countries as follows:

Country for which Crosswalk Index Values Are Available	Enrolling Country in this Study who Will be Mapped to this Country
Denmark	Denmark, Finland, and Sweden
France	Belgium, France, Italy, and Switzerland
Germany	Czech Republic, Croatia, Germany, and Poland
Japan	None
Netherlands	Netherlands
Spain	Spain
Thailand	None
United Kingdom	Ireland and United Kingdom
United States of America	Canada and United States of America
Zimbabwe	None

These crosswalk index score will not be calculated when responses are missing for one or more of the dimensions.

The questionnaire also includes a visual analog scale (VAS), where the subjects will be asked to rate their current health status on a scale of 0-100, with 0 being the worst imaginable health state.

**9.8.3.2. MISSING DATA METHODS FOR OTHER SECONDARY EFFICACY ENDPOINTS**

**9.8.3.2.1. PGIC AND CGIC FOR NARCOLEPSY OVERALL AT THE END OF THE DB  
 RANDOMIZED-WITHDRAWAL PERIOD**

Missing data will not be imputed for these other secondary efficacy endpoints.

**9.8.3.2.2. CHANGE IN SF-36 AND IN EQ-5D-5L SELF-REPORTED QUESTIONNAIRE FROM END OF OL STABLE-DOSE PERIOD TO END OF DB RANDOMIZED-WITHDRAWAL PERIOD**

For subjects without post-randomization SF-36 scale normalized scores and 2 overall components as well as EQ-5D-5L dimension and VAS scores, the result from the OL SDP will be carried forward using a BOCF approach.

**9.8.3.3. ANALYSIS OF OTHER SECONDARY EFFICACY ENDPOINTS**

All other secondary endpoints will be analyzed based on the EFF.

**9.8.3.3.1. PGIC AND CGIC FOR NARCOLEPSY OVERALL AT THE END OF THE DB RANDOMIZED-WITHDRAWAL PERIOD**

Number and percentage of subjects in each PGIC/ CGIC category will be provided.

These other secondary efficacy endpoints will be analyzed using the Cochran-Mantel-Haenszel (CMH) test for row means score difference.

**9.8.3.3.2. CHANGE IN SF-36 FROM THE END OF OL STABLE-DOSE PERIOD TO THE END OF DB RANDOMIZED-WITHDRAWAL PERIOD**

Observed and change from baseline in each of the 8-scale profile of functional health and well-being scores as well as the two overall component summary measures will be summarized using descriptive statistics by visit and analyzed similarly to the primary analysis of the primary efficacy endpoint (see [section 9.8.1.4](#)).

**9.8.3.3.3. CHANGE IN EQ-5D-5L SELF-REPORTED QUESTIONNAIRE FROM THE END OF OL STABLE-DOSE PERIOD TO THE END OF DB RANDOMIZED-WITHDRAWAL PERIOD**

Observed and change from baseline in EQ-5D-5L crosswalk index scores and VAS values will be summarized using descriptive statistics by visit and analyzed similarly to the primary analysis of the primary efficacy endpoint (see [section 9.8.1.4](#)).

Additionally, a shift table from the end of the OL SDP to the end of the DB RWP will be presented for each dimension.

The following information will also be tabulated:

- Number and percentage of subjects by score and by visit,
- Number and percentage of subjects reporting any problem (i.e. score 2 to 5) for each dimension by visit.

## 9.8.4. OTHER EFFICACY ENDPOINT

### 9.8.4.1. OTHER EFFICACY ENDPOINT & DERIVATION

The CGIs is a 7-point Likert-type rating scale and a widely used assessment in clinical psychopharmacology trials to assess severity of illness. The responses of this investigator-completed scale range from 1 = normal, no sign of illness to 7 = among the most extremely ill patients. The Investigator will rate his/her impression of the severity of the subject's narcolepsy overall at the end of the OL SDP relative to his/her experience with this patient population.

### 9.8.4.2. MISSING DATA METHODS FOR OTHER EFFICACY ENDPOINT

Missing data will not be imputed for the CGIs.

### 9.8.4.3. ANALYSIS OF OTHER EFFICACY ENDPOINT

CGIs will be summarized descriptively based on the EFF.

## 9.9. SAFETY OUTCOMES

In general, safety outcomes will be summarized across all study periods by visit overall, and by Pre-Randomization Group based on SAF. Data collected while subjects randomized to placebo were on placebo will be excluded from this summaries.

Data will also be summarized overall and by treatment group based on the DB RWP SAF.

No inferential statistics will be performed; only summary statistics will be provided unless otherwise noted.

### 9.9.1. ADVERSE EVENTS

AEs will be coded to SOC and PT using the MedDRA dictionary, version 19.1 and will be classified as follows:

- **Prior AEs** are defined as AEs that started on or after the signature of the Main Study informed consent but prior to the first dose of OL OTTP study drug;
- **For the overall summaries**, (TEAEs) are defined as any AEs that started or worsened in severity on or after the first dose of Open-Label study drug up to the last dose of study drug during the Open-Label Optimized Treatment and Titration period, Open-Label Stable-Dose Period, Double-Blind Randomized-Withdrawal Period or Open-Label Extension period (whichever is the latest) + 30 days.
- **For the DB RWP**, TEAEs are defined as any AEs that started or worsened in severity on or after the first dose of double-blind study drug up to 1) the last dose of double-blind study drug for subjects who did not enter the Open-Label Extension, 2) the first dose of study drug during the Open-Label Extension for subjects who rolled over into the Open-Label Extension immediately

after having completed the Main Study or 3) whichever occur first between the following two timepoints for subjects who rolled over into the Open-Label Extension after having re-entered into the study: last dose of double-blind study drug or first dose of study drug during the Open-Label Extension.

- **For the Main Study**, TEAEs are defined as any AEs that started or worsened in severity on or after the first dose of study drug up to the first day of the Open-Label Extension period for rollover subjects; or the first day of the Open-Label Extension period or the day of the last dose of study drug in the Double-Blind Randomized-Withdrawal period + 30 days (whichever is the earliest) for re-entry subjects.
- **For the OLE**, TEAEs are defined as any AEs that started or worsened in severity on or after the first dose of Open-Label study drug during the Open-Label Extension period up to the last dose of study drug + 30 days.
- **Post AEs** are defined as any AEs that started or worsened in severity after the last dose of study drug during the OTTP, SBP, RWP or OLE (whichever is the latest) + 30 days.

For OLE re-entry subjects, AEs occurring after their last dose of DB study drug, but prior to their first dose of OLE study drug will be considered as post AEs .

Only TEAEs will be summarized, but all AEs will be presented in the subject data listings.

In addition, TEAEs will be summarized for the Main Study and OLE separately.

An overall summary of the number and percentage of subjects within each of the following categories will be provided:

- All TEAEs
- TEAEs with a severity of severe
- Life-threatening TEAEs
- Fatal TEAEs
- TEAEs related to study drug
- TEAEs with an outcome of death
- Serious TEAEs
- TEAEs leading to discontinuation of study drug

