5.1.1.2 Placebo

A matching oral solution to JZP-258 will be provided. The placebo formulation is an aqueous solution consisting of sodium citrate, malic acid and sucralose. All ingredients are compendial (USP/NF).

Placebo treatment is applicable to the Double-Blind Randomized-Withdrawal Period only.

Treatments Administered 5.1.1.3

During the Optimized Treatment and Titration Periods all subjects will receive open-label JZP-258.

Pre-randomization Groups 1 and 2

Subjects entering the study on Xyrem alone or on Xyrem plus an additional anticataplectic will be switched from their current dose of Xyrem to JZP-258 on a gram to gram straight conversion at the start of the Optimized Treatment and Titration Period and remain on that dose for 2 weeks. If further titration is needed, titration will proceed at a rate of 1 or 1.5 g per night per week during this period not to exceed a total dose of 9 g per night.

Pre-randomization Groups 3 and 4

Subjects entering the study receiving treatment with a non-Xyrem anticataplectic only or not treated with any anticataplectic agent will receive an initial dose of JZP-258 4.5 g per night at the start of the Optimized Treatment and Titration Period. Dose adjustments will proceed at a rate of 1 or 1.5 g per night per week until a tolerable dose of JZP-258 is reached over a period of 2 weeks. If needed, the dose of JZP-258 may be further titrated to a stable, tolerable, and effective dose that does not exceed a total dose of 9 g per night.

Pre-randomization Groups 2 and 3 will taper anticataplectics as described in Section 3.1.

During the Stable-Dose Period subjects will receive open-label JZP-258 at the same unchanged dose that they received during the last 2 weeks of the Optimized Treatment and Titration Period.

> Confidential Page 45 of 148

All subjects will receive blinded study drug during the Double-Blind Randomized-Withdrawal Period. At the end of the Stable-Dose Period, subjects enter the Double-Blind Randomized-Withdrawal and will be randomized 1:1 to receive either JZP-258 at the dose taken during the last 2 weeks of the Stable-Dose Period or JZP-258 placebo (at a volume equivalent to the JZP-258 dose taken in the last 2 weeks of the Stable-Dose Period).

Study drug will be dispensed at clinic visits and, if applicable, at intervals specified by state or local regulations or to resolve logistical issues.

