7.1.5 End of Double-Blind Randomized-Withdrawal Period or Early Termination

End of Week 16 - Visit 16

- Record weight in ordinary indoor clothes (without shoes).
- Obtain vital signs (systolic and diastolic blood pressure, heart rate and respiratory rate, and body temperature) after the subject has been resting for at least 5 minutes.
- Perform a physical examination including a full examination of body systems (excluding a full genitourinary exam) and a brief neurological examination.
- Obtain fasting blood samples for serum chemistry (including Na, K, Ca, and Mg), hematology.
- Collect urine for urinalysis and perform urine drug screen.
- Perform alcohol screen.
- Provide for a light breakfast, if needed.
- Obtain a 12-lead ECG after the subject has been resting supine for at least 5 minutes.
- Complete CGIc for narcolepsy overall.
- Have subject complete the PGIc.
- Obtain a urine pregnancy test for all females of childbearing potential (Section 6.10.1).
- Administer the following:
 - ESS
 - SF-36
 - EuroQoL
 - PHO-9
 - C-SSRS Since Last Visit version.
- Review Cataplexy Frequency Diary for completeness.
- Review the Dosing Diaries for completeness and compliance with dosing.
- Collect remaining study drug from Double-Blind Randomized-Withdrawal Period and assess compliance versus Dosing Diary.
- Record all AEs that occurred since the last visit on the AE eCRF.
- Record all concomitant medications that were taken since the last visit on the concomitant medications eCRF.
- Schedule the Safety Follow-up Visit in 2 weeks if not enrolling into the Open-Label Extension.
- Instruct subject to follow-up with their healthcare provider regarding the resumption of any medications that were discontinued prior to study participation if not enrolling into the Open-Label Extension.

Confidential Page 76 of 148

Jazz Pharmaceuticals

If a subject is withdrawn before completing the study, the reason for withdrawal will be entered on the appropriate eCRF. The specific reason for the withdrawal should be documented on the eCRF. For instance, rather than stating "withdrew informed consent", the specific reason for withdrawing the informed consent should be stated. Whenever possible and reasonable, the evaluations that were to be conducted during the final study visit should be performed at the time of premature discontinuation.

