**ALGORITHM FOR TREATMENT EMERGENCE OF ADVERSE EVENTS**

START DATE	STOP DATE	ACTION
Known	Known, Partial, Missing	
 
• If AE start date or worsened in severity < study drug first dose date, then not TEAE
 
• If study drug first dose date ≤ AE start date or worsened in severity ≤ (study drug last dose date + 30 days), then TEAE
 

Partial, but known components show that it cannot be on or after study drug first dose date	Known, Partial, Missing	Not TEAE
Partial, but known components show that it could be on or after study first dose date	Known	
 
• If AE stop date < study drug first dose date, then not TEAE
 
• If study drug first dose date ≤ AE worsened in severity or stop date ≤ (study drug last dose date + 30 days), then TEAE
 

or	Partial	If known components show that: 
 
• AE stop date < study drug first dose date, then not TEAE
 
• {[Study drug first dose date ≤ AE stop date ≤ (study drug last dose date + 30 days)] or [(study drug last dose date + 30 days) < AE stop date]}, then TEAE
 

Missing	Missing	Assumed TEAE

Note: Missing days will be assumed to be the first day of the month and missing months will be assumed to be the first month of the year for the purposes of determining if a partial date could be on or after the study first dose date (i.e. first day of month if day unknown or 1st January if day and month are unknown),.

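### For placebo-arm subjects who never enter the OLE, the pooled TEAE tables leave out events on placebo but count events after it, with no split by arm

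*SAP*

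**What the plan says.** **Overall window.** SAP 9.9.1 opens the overall TEAE window at the first open-label dose. It closes the window at the latest dose of study drug in any period, naming the "Double-Blind Randomized-Withdrawal Period or Open-Label Extension period (whichever is the latest) + 30 days". The treatment-emergence algorithm in SAP Appendix 2 repeats the rule, with no anchor specific to an arm: "study drug last dose date + 30 days), then TEAE".

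**Placebo is study drug.** Protocol 5.1.1.3 says: "All subjects will receive blinded study drug during the Double-Blind Randomized-Withdrawal Period".

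**Exclusion.** SAP 9.9 presents safety across periods, overall and by Pre-randomization Group, and adds: "Data collected while subjects randomized to placebo were on placebo will be excluded from this summaries". It says nothing about data collected after the last placebo dose.

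**Double-blind window.** For subjects who stay out of the OLE, SAP 9.9.1 ends the randomized-withdrawal TEAE window at "the last dose of double-blind study drug for subjects who did not enter the Open-Label Extension".

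**Re-entry subjects.** Events after the last double-blind dose but "prior to their first dose of OLE study drug will be considered as post AEs".

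**What is tabulated.** "Only TEAEs will be summarized, but all AEs will be presented in the subject data listings".

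**After Visit 16.** Protocol 7.1.5 has the site tell subjects to see their healthcare provider about "resumption of any medications that were discontinued prior to study participation if not enrolling into the Open-Label Extension".

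**The concern.** With on-placebo data removed, the across-period tables otherwise describe time on JZP-258 and the tail after it. For one set of subjects the two rules do not fit together. A placebo-arm subject who never enters the OLE has the on-placebo days taken out, and then has a 30-day tail measured from the last placebo dose put back in. The table skips the days just after JZP-258 stopped and resumes later.

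Those later events sit in a pooled column beside events that began on JZP-258 or within 30 days of it, and the reader cannot separate them by arm. Some may start after the subject has resumed Xyrem or another earlier medication. They have no place in the double-blind table either. At stake is the readability of a descriptive safety table; no hypothesis test or power figure depends on it.

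**Working it through.** The plan states no figure to reproduce here. The check is day arithmetic plus a comparison of the definitions.

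**Inputs**
- Double-blind period: 2 weeks; Visits 16 and 17 each have a +3-day window (Protocol 3.1.1.4 and Appendix 1.1).
- Visit 17: 2 weeks after the double-blind period, for subjects not rolling over (Protocol 3.1.1.5).
- AE documentation: to the final study visit or early termination. SAEs the investigator learns of within 30 days of the last dose must also be reported, and related SAEs at any time (Protocol 6.13.6).
- Planned placebo arm: 65 subjects (Protocol 9.3).

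**Timeline for a placebo completer who never enters the OLE.** Day 0 is the last open-label JZP-258 dose; randomization (Visit 15) is day 1.
- Last placebo dose: day 14, or 14 + 3 = 17.
- Visit 16: day 15, or 15 + 3 = 18.
- Visit 17: 15 + 14 = day 29, or at the latest 18 + 14 + 3 = day 35.
- Overall TEAE window closes: 14 + 30 = day 44, or 17 + 30 = day 47.
- For a subject whose last dose was JZP-258, it closes 30 days after that dose. The excess is 44 - 30 = 14 days, or 47 - 30 = 17 days, which is the time on placebo.

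| Days since last JZP-258 | Pooled across-period tables | Double-blind table |
|---|---|---|
| 1 to 14 (17), on placebo | excluded | counted under placebo |
| After the last placebo dose, to Visit 17 (day 29-35) | counted, arms pooled | not counted |
| Visit 17 to day 44-47 | counted; mainly SAEs are collected | not counted |

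**By route after Visit 16**
- *Rollover:* open-label JZP-258 is dispensed at Visit 16 (Protocol 6.11), so later events follow JZP-258. No problem.
- *Re-entry:* the gap events are post AEs, which are listed and not tabulated.
- *Never in the OLE:* neither rule applies, and the post-placebo events are tabulated. Subjects who stop placebo early always fall here, because OLE entry requires completion of double-blind treatment (Protocol 3.1.2). For them the on-placebo interval is shorter than 14 days.

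**Would re-anchoring at the last JZP-258 dose + 30 days repair it?** The window would close at day 30. Routine collection ends at day 29-35, so this removes at most 35 - 30 = 5 days of routine AEs, and none if visits are on schedule. The gap over the on-placebo days would remain.

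**Two related defects in SAP 9.9.1.** The Main Study TEAE definition gives an end for rollover and re-entry subjects and none for subjects who never enter the OLE. For re-entry subjects, it runs to the earlier of OLE day 1 or the last double-blind dose + 30 days. The sentence classing their gap events as post AEs contradicts that.

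**The case against.** The strongest reply is that little is misplaced. On-placebo events are not lost; they appear under placebo in the double-blind table, where they belong. The pooled tables are labelled overall and by Pre-randomization Group, TEAE is a class based on timing, and relationship to study drug is tabulated separately. A 30-day tail is an ordinary rule, and over-inclusion is cautious for safety. All AEs are listed, so the events can be traced. All of this stands, and it keeps the point small. It does not explain why the same interval is tabulated for one placebo subject and only listed for another.

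A reader might also infer more than the documents support:
- *That the whole placebo arm is affected.* Rollover subjects are back on JZP-258, and re-entry subjects have their own rule.
- *That the counted events often follow resumed Xyrem or antidepressants.* The protocol only tells subjects to discuss resumption. It gives no frequency, the instruction covers both arms, and Group 4 entered on no anticataplectic.
- *That the SAP reports these events as JZP-258 TEAEs.* No table is so titled; that reading is inferred from the placebo exclusion.
- *That the short half-life (mean 0.57 hour fasted, 0.62 hour fed, Protocol 1.4.1) settles attribution.* It would argue equally against the 30-day tail in both arms.

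**Conclusion.** The point holds for placebo-arm subjects who never enter the OLE. Their on-placebo events are left out of the pooled tables, and their post-placebo events are counted there with no arm split: routine AEs to about day 29-35 and SAEs to about day 44-47 after the last JZP-258 dose. The double-blind table does not show those post-placebo events, and the treatment of re-entry subjects is inconsistent with this.

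The size is small. The documents do not give the share of subjects who stay out of the OLE, so the number of subjects exposed to the rule lies between 0 and about 65 planned placebo subjects. The number with an event in the interval cannot be derived. The day figures assume nightly dosing, a 2-week double-blind period and visits within the +3-day windows. No efficacy conclusion is touched. It is worth correcting because the written rule misplaces events and the repair is cheap.

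**What to change.** In SAP 9.9.1 and the Appendix 2 algorithm:
1. For placebo-arm subjects who never enter the OLE, exclude from the pooled across-period TEAE summaries any event that starts or worsens on or after the first placebo dose. This matches the on-placebo exclusion and the re-entry rule.
2. Add a small table, by randomized arm, of events starting after the last double-blind dose in all subjects who never enter the OLE, so that none is lost. Note the events that start after a recorded restart of Xyrem or another anticataplectic.
3. State where the Main Study TEAE window ends for subjects who never enter the OLE.
4. Reconcile the 30-day rule for re-entry subjects with the sentence classing their gap events as post AEs.

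The cost is SAP wording, a derivation flag from dates already collected and one small table. Pooled TEAE counts fall slightly. These placebo subjects lose their 30-day tail in the pooled table, while JZP-258-arm subjects keep theirs. That asymmetry is acceptable because the events move to the by-arm table.
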